1- Initiation of randomized treatment at Visit 2 can only begin if the patient meets the criteria for Initiation of Treatment. Please refer to Sections [3.3.2](#) and [3.3.3](#).

2- At Visit 10, Non- Responders (NR) will receive their last study drug administration and Responders (R) will have their End of Study (EoS) visit.

3- Should a patient prematurely discontinue before their scheduled EoS every effort should be made to keep the patient in the trial and complete all of the remaining study visits or at a minimum an early EoS visit. Patients who prematurely discontinue before V7/Wk16 are considered Non-Responders.

4- C = Complete Physical Examination (PE) includes general appearance as well as evaluation of all organ systems; T = Targeted physical examination includes evaluation of organ systems associated with AE(s) symptoms or laboratory abnormalities. At Visit 10 complete physical examination will be performed for Responders (EOS), targeted physical examination will be performed for Non-Responders. Please refer to Section [5.2.1](#).

5- Vital signs will be assessed at predose, at approximately 5 minutes after the end of infusion, and 60 mins after the end of infusion at visits with i.v. administration.

6- Safety laboratory tests include clinical chemistry, haematology, coagulation, and urinalysis, and will be performed centrally. Local Labs may be used for dosing decisions prior to i.v. administration. Please refer to Section [5.2.3](#).

7- Only applicable for women of childbearing potential. S – serum pregnancy test (performed at screening). U – urine pregnancy tests will be performed at all other visits indicated in the [Flow chart](#). Urine pregnancy testing should be done prior to administration of study drug. Study drug should only be administered in case of a negative test result. (S) - in case of a positive urine pregnancy test, a serum pregnancy test will be done. Please refer to Section [5.2.5.2](#).

8- ECG measurements should always precede blood sampling and drug administration. Clinically significant abnormal findings should be reported as AEs in the eCRF.

9- Infection testing includes tuberculosis, hepatitis B, hepatitis C, and HIV assessments. Please refer to Table [5.2.3: 1](#). For the EoS visit only tuberculosis and hepatitis B testing will be performed. For Responders the Infection testing will be conducted at V10 (Week28) which corresponds to their EoS. For Non Responders the Infection testing will be conducted at V11.

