7.3.4 Safety analyses

Adverse events will be coded using the Medical Dictionary for Drug Regulatory Activities (MedDRA). Standard BI summary tables and listings will be produced. All adverse events with an onset between start of treatment and end of the residual effect period (REP), a period of 16 weeks after the last dose of trial medication, will be assigned to the on-treatment period for evaluation.

All treated patients will be included in the safety analysis. In general, safety analyses will be descriptive in nature and will be based on BI standards. No hypothesis testing is planned.

Statistical analysis and reporting of adverse events will concentrate on treatment-emergent adverse events, i.e. all adverse events occurring between start of treatment and end of the REP. Adverse events that start before first drug intake and deteriorate under treatment will also be considered as 'treatment-emergent'.

[figure not shown]
Frequency, severity, and causal relationship of adverse events will be tabulated by system organ class and preferred term after coding according to the current version of the Medical Dictionary for Drug Regulatory Activities (MedDRA) at database lock.

[figure not shown]
Laboratory data will be analysed both quantitatively as well as qualitatively. The latter will be done via comparison of laboratory data to their reference ranges. Values outside the reference range as well as values defined as clinically relevant will be summarised. Treatment groups will be compared descriptively with regard to distribution parameters as well as with regard to frequency and percentage of patients with abnormal values or clinically relevant abnormal values.

Vital signs, physical examinations, or other safety-relevant data observed at screening, baseline, during the course of the trial and at the end-of-trial evaluation will be assessed with regard to possible changes compared to findings before start of treatment.

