6. GENERAL ANALYSIS DEFINITIONS

6.1 TREATMENTS

For basic study information on the treatment to be administered, assignment to treatment, and selection of dose, cf. Section 4 of the CTP.

In the blinded treatment phase, all patients will receive either intravenous doses of 600mg of BI 655130 solution for infusion (at weeks 0, 4, 8, and 12), or Placebo.

At Week 16, all patients will be evaluated with the EASI Score. Non-responders (EASI < 75) will be re-allocated to receive BI open label trial drug from Week 16 through Week 28; they will be followed until Week 44. Responders (EASI >= 75) will be re-assigned to receive no further trial treatment but will be expected to come to all visits up to Week 28, when EOS visit is planned.

The following trial periods/phases are defined:

Table 6.1: Flow chart of trial period/phases

Trial phase	Description	Start (included)	End (excluded)
Screening phase	Screening	Date of informed consent	Date of start of first infusion of study drug (day 1).
Blinded Treatment phase	Randomised On-treatment period	Date of start of infusion of first study drug (Day 1)	Week 16 visit date + 1 day
Open label Treatment phase ¹	Re-allocation period (Either open label BI655130 or No treatment)	Week 16 visit date + 1 day	Date of EoS Participation visit + 1 day

Dates are defined individually per patient. If more than one date is associated with a specific visit, measurements associated with a specific date are assigned to a study analysis phase according to the rules specified in the table. An analysis phase will not extend beyond the start date of the following phase.

¹ Non-responders (i.e. EASI<75) at Week 16 will be re-allocated to BI655130 600mg IV open label and will continue in the trial until Week 44. Responders (EASI>=75) at Week 16 will be re-allocated to no treatment and will be observed until Week 28 or the day when they return to a 50% reduction in EASI score (EASI50) and start the treatment in the extension trial.

Patients who discontinue the treatment but will continue on trial visits will be included in analyses with the available data. For patients who discontinue trial prematurely only available data will be used in the analyses.

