For the final analysis of the trial to be performed once all patients have completed through the planned period, results will be summarized including the data from the reallocation period (Open-label Treatment phase). Results will be presented separately and in descriptive manner. The time windows for data presentation in this analysis are described in [Table 6.7: 1](#). In addition, analyses including the data from the double-blind period (initially used for the Primary Analysis) will be re-run after the final database lock.

To distinguish between assignment to trial periods/phases and AE assignments, please, refer to [Table 6.1:2](#).

Table 6.1: 2 AE assignment to analysis treatment groups

Randomised treatment	EASI75 response at Week 16	Open-label period	AE assignment to analysis treatment group
PLACEBO	Responder	No Treatment	AE that occurred between first randomised study drug intake and min[(EoS visit date), (last randomised study drug administration date + 112 days)] will be analysed under PLACEBO. AEs occurring later will be listed only.
PLACEBO	Non-Responder	BI 655130 Treatment	AE that occurred between first randomised study drug intake and Week 16 visit date (excluding) will be analysed under PLACEBO. AEs occurring later will be analysed under Open-label BI Treatment.
BI 655130	Responder	No Treatment	AE that occurred between first randomised study drug intake and min[(EoS visit date), (last randomised study drug administration date + 112 days)] will be analysed under BI 655130. AEs occurring later will be listed only.
BI 655130	Non-Responder	BI 655130 Treatment	AE that occurred between first randomised study drug intake and Week 16 visit date (excluding) will be analysed under BI 655130. AEs occurring later will be analysed under Open-label BI Treatment.

Treatment groups up to Week 16 will be labelled as follows:

- **"Speso 600 mg IV q4w"** (i.e., patients randomised to BI 655130 600 mg)
- **"Placebo"** (i.e., patients randomised to Placebo)
- **"Overall Total"** (across treatments: Placebo and BI 655130 600 mg), where appropriate.

Treatment groups for the efficacy analysis after week 16 will be labelled as follows:

- **"Open-label treatment: No Treatment"**
 - **"Placebo"** (i.e., patients randomised to Placebo in the double-blind treatment period and who did not receive an open-label BI 655130 treatment starting from Week 16 (V7))

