 - **"Speso 600 mg IV q4w"** (i.e., patients randomised to BI 655130 in the double-blind treatment period and who did not receive an open-label BI 655130 treatment starting from Week 16 (V7))
 - **"Total"** (i.e., patients randomised either to Placebo or BI 655130 in the double-blind treatment period and who did not receive an open-label BI 655130 treatment starting from Week 16 (V7))
- **"Open-label treatment: Speso 600 mg IV q4w"**
 - **"Placebo"** (i.e., patients randomised to Placebo in the double-blind treatment period and received an open-label BI 655130 treatment starting from Week 16 (V7))
 - **"Speso 600 mg IV q4w"** (i.e., patients randomised to BI 655130 in the double-blind treatment period and received an open-label BI 655130 treatment starting from Week 16 (V7))
 - **"Total"** (i.e., patients randomised either to Placebo or BI 655130 in the double-blind treatment period and received an open-label BI 655130 treatment starting from Week 16 (V7))

Treatment groups for the safety analysis for the whole trial will be labelled as follows:

- **"Speso 600 mg IV q4w"** (i.e., patients randomised to BI 655130 600 mg)
- **"Placebo"** (i.e., patients randomised to Placebo)
- **"Total Speso 600 mg IV q4w OL"** (i.e., patients randomised either to Placebo or BI 655130 600mg and assigned to BI 655130 600 mg open-label treatment at Week 16)

More details on the technical implementation of these analyses are provided in the ADS Plan of this TSAP.

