6.3 SUBJECT SETS ANALYSED

The following analysis sets will be defined for this trial:

- Enrolled set (ES)
This patient set includes all patients who signed informed consent. It will be used for display of patient disposition.
- Randomized set (RS)
This patient set includes all patients who were randomized into the trial. It will be used for display of patient disposition, baseline and demographic characteristics, and patients with IPDs.
- Safety analysis set (SAF)
This patient set includes all randomized patients who received at least one dose of study drug. It will be the main analysis set for presentation of safety. Treatment assignment will be based on the actual treatment administered. Actual treatment refers to the actual treatment administered at the first dosing. This treatment should be followed through the whole trial, regardless of the initially randomised treatment.

- Safety analysis set in the open-label treatment period (SAF-OL)
This patient set includes all randomized patients who received at least one dose of study drug and received study medication after re-allocation visit (i.e., after Week 16 visit). Treatment assignment will be based on the actual treatment administered starting from Week 16 visit. This analysis set will be the main set for presentation of the safety data for the treatment re-allocation period.
- Full analysis set (FAS)
This patient set includes all patients in the SAF who had a baseline measurement for the primary endpoint. It will be the main analysis set for presentation of efficacy results. Treatment assignment will be as randomized.
- Full analysis set including completers (FAS-C)
This analysis set includes all patients in the FAS who completed double-blind treatment, i.e., did not prematurely discontinue treatment up to (and including) Week 12.
- Pharmacokinetic parameter set (PKS)
This patient set includes all patients in the SAF who provide at least one evaluable observation for the BI 655130 concentration, which was not flagged for exclusion. This patient set will be used for the display of concentrations.

The discussion of all exceptional cases and problems and the decisions on the allocation of patients to populations will be made at latest at the DBLM.

Handling of Treatment Misallocations in Analysis Sets

If a patient was administered incorrect treatment during the study, then for safety the following will be used in addition:

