7.8 SAFETY ANALYSIS

All safety analyses will be performed based on the SAF following BI standards. No hypothesis testing is planned.

In addition, overall AE table and the frequency table of patients with at least one AE by MedDRA System Organ Class and Preferred Term will be prepared for AEs occurring between start date of study medication and Week 16 visit data (not including residual effect period).

All safety data analyses beyond Week 16 (for patients not receiving BI open-label treatment) will be based on SAF-OL.

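### SAP 7.8 assigns patients without open-label drug to a safety set that excludes them, and Table 6.1: 2 has no adverse event rule for a Non-Responder who gets no open-label dose (minor)

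*SAP*

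**What the plan says.** **Analysis sets.** SAP 7.8 opens by basing all safety analyses on SAF. It then adds: "All safety data analyses beyond Week 16 (for patients not receiving BI open-label treatment) will be based on SAF-OL". SAP 6.3 limits SAF-OL to treated patients who "received study medication after re-allocation visit (i.e., after Week 16 visit", with treatment taken as what was actually given from Week 16. SAP 6.3 also makes SAF-OL the main safety set for the re-allocation period, although Table 6.1: 1 counts untreated patients in that period.

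**Adverse event assignment.** Table 6.1: 2 has four rows: in each randomised arm, Responder with no treatment and Non-Responder with BI 655130.
- Responder events stay under the randomised arm until the earlier of EoS and last randomised dose plus 112 days, and are only listed after that.
- Non-Responder events stay under the randomised arm up to, but not including, the Week 16 visit date. Then: "AEs occurring later will be analysed under Open-label BI Treatment".

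**Group labels.** SAP 6.1 defines the open-label safety group, 'Total Speso 600 mg IV q4w OL', as patients "assigned to BI 655130 600 mg open-label treatment at Week 16". The efficacy groups just above it use patients who "received an open-label BI 655130 treatment starting from Week 16 (V7".

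**Early stoppers.** Protocol Flow Chart footnote 3 says: "Patients who prematurely discontinue before V7/Wk16 are considered Non-Responders". Protocol 3.3.4.1 keeps them in the trial if they agree. SAP 6.1 says: "Patients who discontinue the treatment but will continue on trial visits will be included in analyses with the available data". Protocol 7.3.4 takes events up to the end of the residual effect period, "a period of 16 weeks after the last dose of trial medication, will be assigned to the on-treatment period for evaluation".

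**The concern.** The rules do not fit together for a patient who receives no open-label drug.

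1. The set named in SAP 7.8 for these patients cannot contain them.
2. A Non-Responder without an open-label dose matches no row of Table 6.1: 2. If the programmer keys on response status alone, the Non-Responder row applies and later events count under open-label BI 655130. For a patient randomised to placebo, that means events attributed to a drug the patient never received.
3. The open-label safety group is labelled by assignment, while SAF-OL is defined by receipt.

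At stake is where some events after Week 16 appear in the summaries: under the double-blind arm, under open-label BI 655130, or nowhere except a listing. Drug-related adverse events are a secondary endpoint (SAP 7.5.2.2), so their attribution should not be left to be settled while the tables are programmed. The SAP 7.8 sentence covers all safety data, and SAP 7.8.2 and 7.8.3 also analyse laboratory values and vital signs separately for the re-allocation period, so those displays share the set problem.

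**Working it through.** The plan states no figure to reproduce. The check has two parts.

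**Part 1: does every combination have a rule?** Cross randomised arm, Week 16 response and open-label dosing (2 x 2 x 2 = 8 cells). Each line below stands for both arms.

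| Week 16 response | Open-label dose | Row in Table 6.1: 2 | In SAF-OL |
|---|---|---|---|
| Responder | No | Yes | No |
| Responder | Yes | No | Yes |
| Non-Responder | No | **No** | No |
| Non-Responder | Yes | Yes | Yes |

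- Four of the eight cells have a row.
- All four cells without an open-label dose lie outside SAF-OL, so the population named in SAP 7.8 is empty.
- A Responder given open-label drug would be a misallocation, which Table 6.2: 1 lists as a protocol deviation (F2.03). The design does not produce it.
- An undosed Non-Responder, by contrast, follows directly from footnote 3 and protocol 3.3.4.1.

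**Part 2: how much follow-up lies beyond Week 16 but inside the residual effect period?**

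Inputs: planned dose days 1, 29, 57 and 85 (V2, V4, V5, V6) and planned Week 16 visit on Day 113 (protocol Flow Chart); residual period 16 x 7 = 112 days (protocol 7.3.4).

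Formula: days past Week 16 = (last dose day + 112) - 113. Share = days past Week 16 / 112.

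| Last dose | Residual period ends | Days past Day 113 | Share of 112 days |
|---|---|---|---|
| Day 1 | 1 + 112 = 113 | 0 | 0% |
| Day 29 | 29 + 112 = 141 | 28 | 25% |
| Day 57 | 57 + 112 = 169 | 56 | 50% |
| Day 85, no Week 16 dose | 85 + 112 = 197 | 84 | 75% |

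The Flow Chart allows plus or minus 3 days both at the dosing visits after Day 1 and at Week 16. The two windows together move the last three results by up to 6 days either way: 22 to 34, 50 to 62 and 78 to 90 days. For a Day 1 dose only the Week 16 window matters, giving 0 to 3 days. All figures are maxima, because an earlier EoS shortens them. They are calendar days per affected patient, not event counts.

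**Responders as a cross-check.** A Responder last dosed on Day 85 is covered to Day 85 + 112 = 197, which is the planned Week 28 EoS. The Responder rows therefore cover that patient's whole planned follow-up.

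**Can such patients occur?** Protocol 1.2.3 reports discontinuations of trial drug for adverse events in the earlier palmoplantar pustulosis trial with four-weekly dosing: 3 on placebo, 1 on 300 mg and 3 on 900 mg, among 59 patients. Disease and doses differ, and not all such patients would stay in follow-up. This shows that the case is plausible; it is not an estimate for this trial.

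**The case against.** **The 'not' is one stray word.** Without it, SAP 7.8 agrees with SAP 6.3, and untreated patients fall back to SAF under the opening sentence of 7.8. This is very likely what was meant. It does not supply the missing table row or change the group label.

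**SAF-OL already protects its own tables.** Membership requires a dose after re-allocation and treatment is as actually given. An undosed patient therefore cannot enter a table run on SAF-OL, whatever the group label says. This stands and reduces the label conflict to a wording matter. A reader might infer that undosed patients will in fact be counted among those exposed to open-label drug. The documents do not support that: it follows only if Table 6.1: 2 is applied by response status and the set definition is disregarded.

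**There is a parent rule and a route for odd cases.** The SAP says it builds on protocol Section 7, and protocol 7.3.4 already gives the residual period rule. SAP 6.3 sends exceptional cases, and decisions on which population a patient belongs to, to the database lock meeting at the latest. SAP 6.1 refers technical details to an ADS Plan that is not among the documents. All this makes sensible handling likely. Still, Table 6.1: 2 exists to state the assignment, and here it states none, or the wrong one.

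**A reader might also infer that safety data of all untreated patients are lost after Week 16.** They are not. The Responder rows cover the adverse events of the main untreated group, and SAP Section 7 lists all individual values.

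**Conclusion.** The point holds as a minor inconsistency. The SAP 7.8 sentence contradicts the SAF-OL definition, probably through a slip. Table 6.1: 2 lacks a rule for a Non-Responder with no open-label dose, and its nearest row would give the wrong attribution. The open-label safety label conflicts with SAF-OL, but SAF-OL governs in tables run on it.

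For each affected patient, at most 28, 56 or 84 days of the 112-day residual period are involved at planned visit days, depending on the last dose, and none after a Day 1 dose only. The number of patients is not in the documents and may be zero. The effect is confined to descriptive adverse event, laboratory and vital-sign displays that extend beyond Week 16. Efficacy analyses, the additional adverse event tables limited to first dose through Week 16, and the listings are unaffected. Nothing in the documents shows that a safety conclusion of the trial would change.

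This rests on the SAP text alone. The wording conflict is certain. What would happen to the data in practice is not, since the ADS Plan may already resolve it.

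**What to change.** Change the SAP only.

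- **SAP 7.8.** Delete 'not', so that SAF-OL applies to patients who receive open-label BI 655130. Add that patients who do not receive it remain in SAF under their SAF (actual) double-blind treatment. Their adverse event, laboratory and vital-sign data after Week 16 are summarised under that group to the earlier of EoS and last dose plus 112 days, and only listed after that. This should be written out in 7.8, because Table 6.1: 2 is keyed to randomised treatment and covers adverse events only.
- **Table 6.1: 2.** Add one row per arm for a Non-Responder with no open-label dose, using the existing Responder rule.
- **SAP 6.1.** Define 'Total Speso 600 mg IV q4w OL' as patients who received at least one open-label dose of BI 655130.

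The cost is one corrected sentence with a short addition, two table rows and one group definition. No protocol amendment, extra data or extra visits are needed.

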7.8.1 Adverse events

AEs will be coded with the most recent version of MedDRA.

The analyses of AEs will be descriptive in nature. All analyses of AEs will be based on the number of patients with AEs and not on the number of AEs. System organ classes (if applicable) will be sorted according to the standard sort order specified by the EMA, preferred terms (if applicable) will be sorted by total frequency (within system organ class) across all treatment arms.

The analyses of AEs will be performed for double-blind period and for the re-allocation period separately.

For further details on summarization of AE data, please refer to “Analysis and Presentation of Adverse Event data from Clinical Trials” [BI-KMED-BDS-HTG-0066] (7) and “Handling of missing and incomplete AE dates” [BI-KMED-BDS-HTG-0035] (4).

The analysis of AEs will be based on the concept of treatment emergent AEs. If only the start date of an AE is collected (without start time), any AE occurrence on the same day as the first BI 655130 administration will be assigned to the on-treatment phase.

An overall summary of AEs will be presented by treatment.

This overall summary will include summary statistics for the class of other significant AEs (sponsor definition based on ICH E3 (9)) and for the class of AESIs.

The following is considered an AESI in this trial:

- Hepatic injury
- Infusion reactions including anaphylactic reaction
- Severe infections
- Opportunistic and mycobacterium tuberculosis infections

The investigator has to classify on the eCRF whether an observed AE was an AESI or not. Only those AEs that are indicated by the investigator as AESI in the eCRF will be analysed in this category.

Based on the specification provided in ICH E3 (9), the sponsor has defined AEs which are to be classified as ‘other significant’. These will include those non-serious AEs which were reported with ‘action taken = Drug withdrawn’ or ‘action taken = Dose reduced’.

The frequency of patients with AEs will be summarised by treatment, primary system organ class and preferred term. AEs which were considered by the investigator to be drug related will be summarised separately (secondary safety endpoint of this trial). Separate tables will also be provided for patients with SAEs, patients with drug-related SAEs, patients with AESIs, patients with AE leading to discontinuation of the trial, and patients with other significant AEs (as described previously). AEs will also be summarized by maximum RCTC grade.

A summary of user-defined AE concepts (UDAEC) will be presented by treatment group. The UDAEC are presented in the table below.

Table 7.8.1: 1 Project MEDDRA search criteria for User Defined Adverse Event Concepts

User Defined AE Concepts	Categories
Infusion/Systemic hypersensitivity reactions including anaphylactic reactions	Narrow SMQ “Anaphylactic reaction” Narrow SMQ “Angioedema” Narrow SMQ “Hypersensitivity”
Severe infections (according to RCTC grading)	SOC Infections and infestations of at least severe RCTC grade, by HLGT
Opportunistic infections	MedDRA SMQ Opportunistic Infections (narrow)
Hepatic injuries	See Section 7.8.2
Tuberculosis infections	BIcMQ sub-search 8.2 “Tuberculosis related terms”
Malignant tumours	(SMQ “Malignancies”) (Sub-SMQ “Malignant or unspecified tumours”) Narrow Sub-SMQ “Malignant tumours” Narrow Sub-SMQ “Haematological malignant tumours” Narrow Sub-SMQ “Non-Haematological malignant tumours”
Torsades de pointes	Broad SMQ “Torsades de pointes/QT prolongation”
Malignant skin tumours	(SMQ “Skin neoplasms, malignant and unspecified”) Broad Sub-SMQ “Skin malignant tumours”
Skin melanomas	HLT Skin melanomas (excl. Ocular)
Non-melanoma skin cancer (NMSC)	Broad Sub-BIcMQ “Skin Malignancies excluding melanomas”
Malignancies excluding NMSC	Sub-SMQ “Malignant tumours” excluding broad sub-BIcMQ “Skin Malignancies excluding melanomas”

For disclosure of AE data on ClinicalTrials.gov, the frequency of patients with non-serious AEs occurring with an incidence of greater than 5% (in preferred terms) will be summarised by treatment, primary system organ class and preferred term. The frequency of patients with SAEs will also be summarised.

